#### 3.6.1. Analysis of Adverse Events

Analyses of safety data will use the safety population and will only be conducted for SAEs, related SAEs, AESI, and laboratory values.

#### **Adverse Events of Special Interest:**

- Iron overload is defined as any liver biopsy findings or MRI imaging consistent with this diagnosis in the setting of persistent TSAT >45%.
- Clinically significant hypophosphatemia, defined as serum phosphorus <2.5 mg/dL.

No statistical inference testing will be done for adverse events.

AE analyses, by subject incidence and event counts, will be summarized by preferred terms, within system organ class, by number and percentage for all subjects in the safety population.

All SAEs will be coded using Medical Dictionary for Regulatory Activities (MedDRA). All verbatim terms will be reconciled to preferred terms by the Medical Monitor. Treatment-emergent SAEs will be summarized by system organ class and preferred term (PT) for each treatment group. SAEs will also be summarized by their maximum severity.

A summary and listing of all deaths and cause of death will be provided overall and by treatment group.

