## **5.0 STUDY DESIGN**

### **5.1 Overall Design**

This is an investigator-initiated multicenter, randomized, double-blind, placebo-controlled, pragmatic clinical trial in patients with advanced CKD to determine the effect of ferric citrate versus matching placebo on the time to a composite endpoint of maintenance dialysis or all-cause mortality.

Subjects who meet all inclusion and none of the exclusion criteria will be randomized in a 1:1 ratio (stratified by site and eGFR) to receive either ferric citrate or matching placebo. All subjects will receive a fixed dose of 2 tablets orally taken with meals or snacks up to 3 times per day. The maximum daily dose is 6 tablets/day. Subjects will remain on study drug for up to 9 months followed by an additional 30-day safety follow-up period. Study drug will be stopped for subjects who initiate maintenance dialysis or receive a kidney transplant. Subjects who undergo maintenance dialysis or receive a kidney transplant will be removed from study with no follow-up visit, however, these subjects will have a vital status check (to ascertain mortality) performed at 30-days following the relevant event.

The study periods are:

- Screening Period: Up to 45 days prior to Day 1. Standard of Care (SOC) laboratory collection permitted up to 45 days (up to 90 days for eGFR) prior to Day 1.
- Treatment Period: Up to 9 months
- Safety follow-up Period: 30 days after EOT

Each randomized subject will complete 5 study visits (2 in-person and 3 phone/virtual or in-person). In-person study visits should attempt to coincide with routine standard of care office visits and relevant clinical data from such standard of care visits (including assessments for possible endpoint events or adverse events) will be collected and entered into the electronic case report form (eCRF). Standard of care (SOC) laboratory assessments as ordered by the primary nephrologist will be utilized. Iron status and serum phosphate collection and monitoring will be required as part of the SOC laboratory assessments. Laboratory assessments captured in the eCRF other than a screening pregnancy test for women of child-bearing potential and non-SOC iron and serum phosphorus labs, will utilize local laboratory results.

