#### **9.6.1.2 Serious Adverse Events**

Each AE is to be classified by the Investigator as serious or nonserious. An AE that meets one or more of the following criteria/outcomes is classified as serious:

- Death
- Life-threatening (see below for definition)
- In-patient hospitalization or prolongation of existing hospitalization (see paragraph below on hospitalization)
- Persistent or significant disability/incapacity (see paragraph below on disability)
- Congenital anomaly/birth defect
- Is considered a medically important event not meeting the above criteria, but which may jeopardize a subject, or may require medical or surgical intervention to prevent one of the criteria listed in this definition.

Serious may also include any other event that the Investigator and Investigator-Sponsor judges to be serious. If there is any doubt whether the information constitutes an AE or SAE, the information is to be treated as an SAE.

**Life-threatening** – Any event in which the subject was at risk of death at the time of the event; ‘life-threatening’ does not refer to an event which hypothetically might have caused death if it were more severe. For example, drug-induced hepatitis that resolved without evidence of hepatic failure would not be considered life-threatening, even though drug-induced hepatitis of a more severe nature can be fatal.

**Hospitalization** – Hospitalization is defined as an overnight admission with observation of a minimum of 24 hours. A hospitalization planned before the start of the study for a pre-existing condition that has not worsened during the AE reporting period does not constitute an SAE unless an untoward event occurs related to the procedure (e.g., elective hospitalization for a total knee replacement due to a preexisting condition of osteoarthritis of the knee that has not worsened during the course of the study).

**Disability** – Defined as a substantial disruption in a person’s ability to conduct normal life functions.

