**The following guidelines are to be used when reporting SAEs for this study:**

**Medical Diagnoses** – Whenever possible, a medical diagnosis term should be used to report SAEs instead of signs and symptoms due to a common etiology, as determined by qualified medical study staff. Signs and symptoms should be reported as event terms only when the medical diagnosis remains unknown and revised to a medical diagnosis term once it has been established.

**Procedures** – Diagnostic and therapeutic non-invasive and invasive procedures, such as surgery, should not be reported as SAEs. However, the medical condition for which the procedure was performed should be reported if it meets the definition of an SAE. For example, when a subject is hospitalized for an acute appendicitis that begins during the SAE reporting period, appendicitis should be reported as the SAE and the resulting appendectomy noted in the narrative.

Pre-planned therapeutic procedures or surgeries not associated with a new medical condition or worsening pre-existing condition should not be reported as SAEs.

The only procedures to be captured include the placement of dialysis access (e.g., Arteriovenous Graft or Fistula [AVG/ AVF], Peritoneal Dialysis [PD] Catheters, Central Venous Catheters [CVC]). Diagnostic procedures (e.g., x-rays, ultrasounds, echocardiograms) are not required to be captured.

**Transplantation** – It is anticipated that subjects may receive a kidney transplant during this study. Kidney transplant will be captured as a Study Endpoint and will not be recorded as an SAE. Adverse events resulting in prolongation of hospitalization during the index kidney transplant will be captured as an SAE. Subjects will discontinue study drug following receipt of a

kidney, other solid organ, hematopoietic stem cell or bone marrow transplant. Receipt of a kidney transplant will be considered an exception to the requirement for a 30-day safety follow up period, however any subject who receives a kidney transplant, and has not withdrawn consent from study participation, will have a vital status check performed at 30-days following the kidney transplant.

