**Dialysis Initiation** - It is anticipated that subjects may initiate maintenance dialysis during this study. Dialysis initiation will be captured as a Study Endpoint and will not be recorded as an SAE. Hospitalization days will be recorded in the eCRF and adverse events resulting in prolongation of hospitalization during the index dialysis initiation will be captured as additional SAEs. Subjects will discontinue study drug following initiation of dialysis. Initiation of dialysis will be considered an exception to the requirement for a 30-day safety follow up period, however any subject who initiates maintenance dialysis, and has not withdrawn consent from study participation, will have a vital status check performed at 30-days following the initiation of maintenance dialysis.

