#### **9.6.5    Reporting Period**

SAE and Adverse Events of Special Interest collection will begin from initiation of study drug treatment through the 30-day follow-up visit. Subjects will be followed for protocol required SAEs and Adverse Events of Special Interest until the final required protocol visit or until all drug-related toxicities and Adverse Events of Special Interest and SAEs have resolved (or are considered chronic/stable), whichever is later.

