### **10.1 Sample Size Determination**

The sample size for this study is driven by the primary endpoint, initiation of maintenance dialysis or all-cause mortality and is based on the observed data from the pilot study using nearly identical inclusion and exclusion criteria. The observed rate of the primary composite endpoint in the pilot study (all-cause mortality, maintenance dialysis or kidney transplant) for patients in the standard of care arm was 0.94 events per person-year of follow up. The observed hazard ratio was 0.42 (58% relative risk reduction,  $p=0.002$ ) for the primary composite endpoint when comparing ferric citrate treated patients versus usual care.

Assuming 1 year recruitment and 0.75 years of follow up (9 months) for each individual and a hazard ratio of 0.60 (40% relative risk reduction), a sample size of 400 patients (200 per arm)

provides 90% power with a 2-sided alpha  $p < 0.05$ . Assuming a hazard ratio of 0.50 (50% relative risk reduction), a sample size of 225 patients provides 90% power with a 2-sided alpha  $p < 0.05$ .

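### Collection of new non-fatal SAEs and AESIs stops at dialysis or transplant, so the planned n, % and counts should be accompanied by observed time and rates by arm

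*SAP*

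**What the plan says.** **When collection stops.** Protocol 5.1: "Subjects who undergo maintenance dialysis or receive a kidney transplant will be removed from study with no follow-up visit". The SAE reporting guidelines in Protocol 9.6.1.2 repeat this for each event: "Initiation of dialysis will be considered an exception to the requirement for a 30-day safety follow up period" and "Receipt of a kidney transplant will be considered an exception to the requirement for a 30-day safety follow up period". Two things continue:
- Vital status is checked 30 days after the event.
- SAEs that prolong the index stay are recorded. For dialysis: "adverse events resulting in prolongation of hospitalization during the index dialysis initiation will be captured as additional SAEs". The transplant paragraph has an equivalent rule.

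**Everyone else.** Protocol 9.6.5: "SAE and Adverse Events of Special Interest collection will begin from initiation of study drug treatment through the 30-day follow-up visit". Under Protocol 8.1.2, subjects who stop study drug permanently are asked to remain on the visit schedule.

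**How events are tabulated.** SAP 3.6.1, for the safety population: "by subject incidence and event counts, will be summarized by preferred terms, within system organ class, by number and percentage". The table shells in SAP 5 show n and % with an event for SAEs, related SAEs and AESIs, and for each system organ class. SAP 3.6 states no safety hypotheses, and SAP 3.6.1 rules out inference testing of adverse events.

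**Time-based analyses elsewhere.** SAP 3.4.5 plans Cox models for first SAE hospitalization (with exclusions) and for death. SAP 3.4.6 plans annualized hospitalization rates before dialysis. SAP 3.6.1 also plans a summary and listing of deaths by arm. SAP 3.5 counts subjects by reason for ending the study, but does not report observed time.

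**The concern.** Apart from death, the main planned cut-off of safety observation is dialysis, which the drug is meant to delay, or transplant. If the drug works as designed, ferric citrate subjects stay under observation longer. More of their events are then recorded even if the underlying rate is the same in both arms. If the drug hastened dialysis, the difference would run the other way and could mask a higher rate.

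A second effect opposes the first. Protocol 9.6.1.2 says "An AE that meets one or more of the following criteria/outcomes is classified as serious", and death is on that list. Fatal SAEs and SAEs that prolong the index stay therefore increase with the number of subjects whose observation ends. A single n (%) column for all SAEs mixes the two effects.

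The hospitalization and mortality analyses do not reach related SAEs, AESIs, SAEs without hospitalization, or the system-organ-class rows. SAEs and AESIs make up most of the adverse-event evidence, because Protocol 9.6.4 excludes non-serious events other than AESIs.

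**Working it through.** **Inputs from the documents** (Protocol 10.1, SAP 3.1, Schedule of Activities): control rate 0.94 per person-year for death, dialysis or transplant; hazard ratio 0.60; 200 per arm; 270 days of treatment plus 30 days of follow-up. The 0.94 rate suits this purpose because all three of its components end observation.

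**Inputs assumed.** The documents give no SAE rate. I use s = 0.3, 0.6, 1.0 and 1.5 per year, equal in both arms, for SAEs that do not end observation. I write q for the share of observation-ending events that carry one captured SAE (fatal or index-stay), also equal in both arms. Hazards are constant and censoring is independent.

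**1. Reproduce the plan's figure.** Over 0.75 years the event probabilities are 1 − exp(−0.94 × 0.75) = 0.506 and 1 − exp(−0.564 × 0.75) = 0.345, mean 0.4254. Then 400 × 0.4254 = 170.2 events. Freedman's formula gives power Φ(√170.2 × 0.40/1.60 − 1.96) = 90.3%, against 90% stated. For hazard ratio 0.50 and N = 225, power is 88.7% (Freedman) or 90.9% (Schoenfeld). The planning inputs are understood correctly.

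**2. Observed time.** With T = 270/365.25 = 0.739 and F = 30/365.25 = 0.082 years, and hazard l of an ending event:

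mean time = (1 − exp(−lT))/l + exp(−lT) × F

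- Placebo, l = 0.94: 0.533 + 0.041 = 0.574 years, or 114.8 patient-years per 200.
- Ferric citrate, l = 0.564: 0.604 + 0.054 = 0.659 years, or 131.7 patient-years per 200.
- Ratio 131.7/114.8 = 1.15. Observation ends within T for 50.1% and 34.1%.

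Other inputs: ratio 1.19 at hazard ratio 0.50, 1.07 at 0.80, 1.00 at 1, 0.92 at 1.25; and 1.08 at hazard ratio 0.60 with a control rate of 0.5 per year.

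**3. Subjects with at least one SAE.**

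P = 1 − [(1 − q) × l/(l + s) × (1 − exp(−(l + s)T)) + exp(−(l + s)T) × exp(−sF)]

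Example, s = 1.0, q = 0: placebo 1 − (0.369 + 0.220) = 41.1%; ferric citrate 1 − (0.247 + 0.290) = 46.3%. The standard error of a difference is √(Σp(1 − p)/200).

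| s per year | q = 0: placebo / ferric citrate, gap (SE) | q = 10%: gap (SE) | q = 20%: gap (SE) | q at which gap is zero |
|---|---|---|---|---|
| 0.3 | 15.5 / 17.7%, 2.2 (0.6) | 0.7 (0.2) | −0.8 (−0.2) | 15% |
| 0.6 | 28.0 / 31.8%, 3.8 (0.8) | 2.4 (0.5) | 1.1 (0.2) | 28% |
| 1.0 | 41.1 / 46.3%, 5.2 (1.0) | 3.9 (0.8) | 2.7 (0.5) | 42% |
| 1.5 | 53.3 / 59.4%, 6.1 (1.2) | 5.1 (1.0) | 4.0 (0.8) | 57% |

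Gaps are ferric citrate minus placebo, in percentage points.

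**4. Would a rate repair this?** Expected count per subject = s × mean time + q × (1 − exp(−lT)). At q = 0 the count ratio is 1.15 and the rate ratio is 1.00, as it should be. With ending-event SAEs pooled in, the rate overcorrects. At q = 20%, count ratios are 0.98, 1.04, 1.08 and 1.10 across the four values of s; dividing by 1.148 gives rate ratios of 0.85, 0.91, 0.94 and 0.96. At s = 0.3 the crude count is closer to 1 than the rate.

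**5. Hypophosphatemia.** If phosphorus were tested only at Days 90, 180 and 270, the mean number of tests reached would be Σexp(−lt) = 1.92 on placebo and 2.29 on ferric citrate. At an assumed equal 1% to 5% chance per test of a value below 2.5 mg/dL, 1.9% vs 2.3% up to 9.2% vs 10.9% would show an event (0.25 to 0.57 SE). Real test dates vary because visit windows are ±30 days and earlier repeats are allowed.

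**The case against.** The strongest objection is that the planned tables are not wrong. With dialysis, transplant and death as competing events, and setting withdrawals aside, the percentage with an SAE is the cumulative incidence under pre-dialysis observation. Longer time at risk is a real consequence of delaying dialysis. A rate answers a different question. This stands, and it limits the point to a missing supplement.

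The gaps are also small, at most about 1.2 standard errors. They vanish at a hazard ratio of 1. For all SAEs, both size and sign depend on inputs that the documents do not give. This also stands.

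Other safeguards exist: the 30-day vital status check, the summary of deaths, the hospitalization and mortality models, by-subject listings, and shells labelled as a selection. They cover deaths and hospitalizations well. None of them commits the plan to observed time or rates for related SAEs, AESIs or system organ classes.

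A reader might infer that all safety observation ends at dialysis or transplant. The documents do not support that: deaths are still ascertained at 30 days and index-stay SAEs are captured. Nor are SAEs and AESIs the only safety data. Protocol 9.5.2 adds events that require an IND safety report, and Protocol 9.7 adds special situations.

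**Conclusion.** This is a cheap improvement worth considering, not an error in the plan. The difference in observed time follows from the plan's own inputs, constant hazards and independent censoring. Its effect on event percentages depends on the assumed SAE rates. For SAEs that do not end observation, those assumptions give a few points' excess on ferric citrate with no difference in rate.

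A reader might conclude that the tables are biased against ferric citrate, or that they will hide harm. Neither follows. The direction depends on the treatment effect and, for all SAEs, on the unknown share of ending events that carry an SAE. With no safety hypothesis or adverse-event test planned, no formal conclusion of the trial is affected. What is at stake is how readers interpret the descriptive comparison of SAEs, related SAEs and AESIs.

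**What to change.** In SAP 3.6.1 and the SAP 5 shells, keep n (%) and event counts and add by arm:

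1. Total observed time, from first dose to the earliest of dialysis, transplant, death, withdrawal or end of the 30-day follow-up.
2. Rates per 100 patient-years for non-fatal SAEs, related SAEs and AESIs. If first-event rates are shown, stop person-time at the first event.
3. A separate line for SAEs that prolong the index dialysis or transplant stay, identified from SAE and endpoint dates or the narrative and kept out of the rate.

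Leave fatal SAEs out of the rate. The death summary in SAP 3.6.1 and the mortality analysis in SAP 3.4.5 already report them.

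**Cost.** SAP and shell wording and modest programming. The dates for observed time are already needed for the endpoints. Classifying index-stay SAEs takes some extra work, because the protocol describes their capture but names no field that flags them. The rates assume roughly constant risk unrelated to nearness of dialysis, so they supplement n (%) and do not replace it. It is best settled before unblinding.

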### 3.6.2. Safety Sub-Group Analyses

There are no safety subgroup analyses planned. If appropriate, selected safety analyses may be conducted using the subgroups from the primary analyses defined above.

### 3.7. Planned Interim Analyses

There are no planned interim analyses for this study.

### 3.8. Sensitivity / Exploratory Analyses

Primary and secondary endpoint analysis using the mITT population may be conducted using the percentage of time on study a subject received a non-zero dose of study drug as a covariate.

## 5. SELECT TABLE SHELLS

**Table X: Selected Demographic, Clinical, and Laboratory Characteristics at baseline**

Variable	Ferric Citrate	Placebo	Significance
eGFR<15 (%)			
Age (mean year)			
Male (%)			
Race (%)	Black		
	White		
	Other		
Ethnicity (n, %)	Hispanic		
	Non-Hispanic		
CKD Cause (%)	Diabetes		
	Hypertension		
	Glomerular disease		
	Polycystic disease		
	Other		
Comorbidity, %			
ASCVD			
Congestive Heart Failure			
Diabetes			
Hypertension			
Peripheral vascular disease			
Cerebrovascular disease			
Secondary hyperparathyroidism			
Dyslipidemia			
Anemia			
Transplant status, %			
Listed or Referred			
Kidney Failure Risk Equation			
Laboratory (mean±SD)			
Creatinine			
eGFR, ml/min per 1.73m^2			

Ferritin, ng/ml				
TSAT				
Phosphorus				

Notes: Therapies and laboratory values estimated during the screening period, prior to Day 1 of the study. Values to be provided as mean (standard deviation) or proportion (count) as appropriate.

Abbreviations: TSAT, transferrin saturation

**Table X: Primary Outcome Measures**

**Table X: Secondary Outcome Measures**

**Table X: All Adverse Events**

Type of AE	Ferric Citrate (n, % with event)	Placebo (n, % with event)
Serious AEs		
Related Serious AEs		
Adverse Events of Special Interest (AESI)		

Abbreviations: AE, adverse event.

**Table X: Specific Adverse Events**

System Organ Class	Serious AE		Related Serious AE	
	Ferric Citrate (n, % with event)	Placebo (n, % with event)	Ferric Citrate (n, % with event)	Placebo (n, % with event)
Blood and lymphatic system				
Cardiac disorders				
Endocrine disorders				
Eye Disorders				
GI disorders				
General				
Hepatobiliary				
Immune System				
Infections and infestations				
Injury (poisoning)				
Metabolism				
Musculoskeletal				
Neoplasms				

Nervous system				
Psychiatric				
Renal and urinary				
Reproductive				
Respiratory				
Skin				
Vascular				
All Others				

Abbreviations: AE, adverse event.

**Additional tables and figures without specific table or figure shells:**

Study Disposition Table

Consented

Screened

Screen Failures

Early Terminations

Reasons for ET (including endpoints)

Completed 9 months

Endpoints

Safety Follow-Up (10 months)
